3 RESEARCH DESIGN AND METHODS

3.1 Study Design

In addition to questionnaires, the primary study procedures include assessment of:

- i) Screening visit – The participant will undergo a physical examination if one has not been completed within the last 3 months.
- ii) Study day 1 - GI vagal function by sham feeding, autonomic functions, small intestinal permeability test and enteral nutrient infusion of lipids, to be performed in that order, on another day (Charlton 7 CRU)
- iii) Study day 2 – Women of child bearing potential will have a urine pregnancy test within 48 hours before the GI Transit study, Gastric emptying of solids and liquids and small intestinal transit on 1 day (Charlton 7 CRU)
- iv) Study day 3 - Upper gastrointestinal endoscopy with a small amount of fluid and intestinal biopsies

These tests will preferably be performed in the order listed above. (ii) must always be performed before (iv). Ancillary procedures include collection of blood for genetic and epigenetic studies and a stool sample for microbial assessment. Vital signs and nurse assessment will be performed at each visit.

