3.3 Details of Study Assessments

In patients with DM, fingerstick bedside reflectance meter blood glucose concentrations will be assessed during enteral infusion and gastric emptying studies at time 0, every 30 minutes for 2h, then at 120 and 180 minutes. For patients with type 1 and type 2 DM who are treated with insulin, insulin will be given according to the patient's sliding scale. For type 2 DM patients who are not on insulin, no insulin will be given.

i) Screening items include questionnaires (for overall functional GI symptoms [Rome III criteria], severity of dyspepsia [Nepean severity index], gastroparesis cardinal symptom index [GCSI], anxiety and depression [HAD], and autonomic symptoms), blood tests (CBC, glycosylated hemoglobin, fasting glucose, sodium, potassium, bicarbonate, calcium, chloride, phosphorous, AST, total bilirubin, alkaline phosphatase, creatinine, high sensitive C-reactive protein, tissue transglutaminase antibodies, and lipase), and EKG (to be reviewed by study physician). Some patients with diabetes mellitus have low serum lipase. Patients with serum lipase < lower limit of normal (i.e., < 10 IU/ml) will not be eligible to participate in the study.

Study procedures will be conducted over 3 days. Items (ii), (iii), (iv), and (v) below will be performed on the same day preferably before other study procedures. A tentative schedule is as follows: (ii) between 8 and 8.45 am, (iii) between 8.45 am and 11 am, (iv) can start while (iii) is in progress and (v) between 12.30 pm and 3 pm.

ii) Plasma pancreatic polypeptide (PP) response to sham feeding. Pancreatic polypeptide (PP) is secreted by the pancreas in response to hypoglycemia, ingestion of food or sham feeding secondary to vagal nerve stimulation. Vagal nerve injury blocks secretion. This assessment will be performed in the Charlton 7 CRU. Subjects will be fasting with NPO for 8 hours prior to this test. They must abstain from coffee or for 12 hours and stop all cholinergic agents for 48 hours before the test. During the sham feeding test, food is chewed and spit out (not swallowed) . After placement of an IV in the hand or forearm vein for blood draws, this hand will be placed in a hotbox heated to 55°C. Blood will be drawn in a lavender-top (EDTA) tube(s) at -5, 0, 5, 10, 15, 20, 25, and 30 minutes for PP. Spin down, keep specimen cold, and send 1.0 mL (0.5 mL minimum) of EDTA plasma frozen in plastic vial.

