Other important medical events are those that may not be immediately life threatening, but are clearly of major clinical significance. They may jeopardize the subject, and may require intervention to prevent one of the other serious outcomes noted above. For example, drug overdose or abuse, a seizure that did not result in in-patient hospitalization or intensive treatment of bronchospasm in an emergency department would typically be considered serious.

All adverse events that do not meet any of the criteria for serious, should be regarded as **non-serious adverse events**.

Withdrawal criteria

- Inability to place nasoduodenal feeding tube
- Inability to obtain intravenous access
- Severe abdominal discomfort, nausea or vomiting during enteral nutrient infusion
- Severe hyperglycemia (> 400 mg/dl) unresponsive to insulin therapy

Adverse Event Reporting Period

Example

For this study, the study treatment follow-up period is defined as 1 days following the last administration of study treatment. The study period during which adverse events must be reported is normally defined as the period from the initiation of any study procedures to the end of the study treatment follow-up.

Preexisting Condition

A preexisting condition is one that is present at the start of the study. A preexisting condition should be recorded as an adverse event if the frequency, intensity, or the character of the condition worsens during the study period.

General Physical Examination Findings

At screening, any clinically significant abnormality should be recorded as a preexisting condition.

At the end of the study, any new clinically significant findings/abnormalities that meet the definition of an adverse event must also be recorded and documented as an adverse event.

Post-study Adverse Event

All unresolved adverse events should be followed by the sponsor-investigator until the events are resolved, the subject is lost to follow-up, or the adverse event is otherwise explained. At the last scheduled visit, the sponsor-investigator should instruct each subject to report, to the sponsor-investigator, any subsequent event(s) that the subject, or the subject's personal physician, believes might reasonably be related to participation in this study.

Hospitalization, Prolonged Hospitalization or Surgery

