5.2 Recording of Adverse Events

At each contact with the subject, the study team must seek information on adverse events by specific questioning and, as appropriate, by examination. Information on all adverse events should be recorded immediately in the source document, and also in the appropriate adverse event section of the case report form (CRF). All clearly related signs, symptoms, and abnormal diagnostic, laboratory or procedure results should be recorded in the source document.

All adverse events occurring during the study period must be recorded. The clinical course of each event should be followed until resolution, stabilization, or until it has been ultimately determined that the study treatment or participation is not the probable cause. Serious adverse events that are still ongoing at the end of the study period must be followed up, to determine the final outcome. Any serious adverse event that occurs after the study period and is considered to be at least possibly related to the study treatment or study participation should be recorded and reported immediately.

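### The stated adverse-event reporting period ends one day after the infusion, before the biopsy endoscopy in the listed order, and conflicts with the plan's own each-contact rule

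*Combined protocol and SAP*

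**What the plan says.** Section 5.1, under Adverse Event Reporting Period, carries a leftover Example label and then states, for this study, that "the study treatment follow-up period is defined as 1 days following the last administration of study treatment". The next sentence, qualified by the word normally, defines the reporting period as "the period from the initiation of any study procedures to the end of the study treatment follow-up".

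Section 3.1 puts the lipid infusion on study day 1 and scintigraphy on study day 2. The last visit listed is "Study day 3 - Upper gastrointestinal endoscopy with a small amount of fluid and intestinal biopsies". The general order is only preferred, but one sequence is mandatory: "ii) must always be performed before (iv". In that list, item (ii) is study day 1 and item (iv) is the endoscopy. Section 3.3 (vii) adds conscious sedation as required and 15 biopsies from the second part of the duodenum.

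Section 5.2 states the main duty: "All adverse events occurring during the study period must be recorded". For events after the study period, it names only serious ones considered at least possibly related to study treatment or participation. The same section opens with a rule that has no time or severity limit: the team must ask about adverse events at each contact, and all such information should be recorded in the source document and the case report form.

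**The concern.** The window opens with the first study procedure but closes by reference to the study treatment. That suits a trial in which the treatment comes last. Here the randomised infusion comes first and the most invasive procedure, sedated endoscopy with 15 biopsies, comes last in the listed order. A coordinator applying Section 5.1 literally would regard the period of mandatory recording as over before the endoscopy began.

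At stake is whether mild and moderate complications of the biopsy visit, such as minor bleeding, pain or after-effects of sedation, are recorded consistently. Section 4 grades adverse events from 0 to 5 and has safety rates reviewed weekly. If grade 1 and 2 events after endoscopy are recorded for some participants and not for others, those rates understate the burden of the procedure.

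**Working it through.** No sample-size or power figure bears on this point. The check places the window on the visit schedule and then reads the recording rules against the result.

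**Inputs**
- Window end: last administration of study treatment plus 1 day (Section 5.1).
- Study treatment: not defined. Lipid with exendin 9-39 or placebo is the only randomised administration (Section 3.3 (v)), given on study day 1, so I take it to be that.
- Clock time of the infusion: tentatively "v) between 12.30 pm and 3 pm" (Section 3.3).
- Spacing of the three study days: not stated.

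**Where the window closes.** With the infusion ending at about 3 pm on day 1, adding 24 hours gives about 3 pm on the following day. On a calendar-day reading, the window closes at the end of that following day.

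**Where the visits fall**
1. Listed order, consecutive days. Scintigraphy is 1 day after the infusion, so wholly or partly inside. Endoscopy is 3 − 1 = 2 days after, so outside.
2. Listed order, with scintigraphy two or more days after the infusion. Both visits are outside.
3. Scintigraphy before the infusion, which is allowed because the order is only preferred. Scintigraphy is inside, since the window opens with the first procedure.
4. Endoscopy on the day after the infusion, which is not barred. The procedure may be inside, but a complication appearing a day or more later is outside.

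In the listed order, then, endoscopy is outside the window at any spacing. Scintigraphy is outside only under some orders and spacings.

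**Which recording rule then applies**
- An event seen at the endoscopy visit: the each-contact rule in Section 5.2 requires it to be sought and recorded. The sentence that ties mandatory recording to the study period does not reach it. The two rules give different answers.
- A serious, possibly related event after the visit: Section 5.2 expressly requires recording and reporting. There is no gap.
- A non-serious event after the visit: in the listed order no further visit is scheduled. Section 5.1 has participants told at the last visit to report later events they believe related to participation, so capture depends on their doing so. If they do, Section 5.2's post-period sentence does not require recording of a non-serious event, although the call could be treated as a contact.

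**Do other provisions fill the gap?**
- Section 4 documents reported events that are serious and expected, or unexpected at any severity. Expected non-serious events are not covered.
- The end-of-study rule in Section 5.1 covers new clinically significant findings, not every mild event.
- The two-week home diary (Section 3.3 (x)) is a gastroparesis symptom index, and its timing relative to the endoscopy is not given.
- The risk-monitoring paragraphs in Section 4 have no entry for endoscopy or biopsy.

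**The case against.** The strongest reply is that a reader might infer that endoscopy complications in general escape recording, and the documents do not say that. The each-contact rule has no time or severity limit, the endoscopy visit is a contact, and Section 3.1 requires vital signs and a nurse assessment at every visit. Non-serious events seen on the day are therefore covered. This stands, and it confines the practical loss to what appears after participants leave.

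A reader might also infer that the hold rule under Stopping Rules rests on incomplete data. It does not. That rule is triggered by perforation or clinically significant bleeding during endoscopy or lipid infusion, and it is not tied to the reporting period. Minor bleeding would not trigger it, and serious related events must be reported whenever they occur.

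Nor can it be said that scintigraphy always falls after the window. The visit order is only preferred and the spacing is not stated.

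Finally, the wording is soft: the period is only normally so defined, it sits under an Example label, and study treatment is undefined. If that term were meant to include every study procedure, the conflict over the endoscopy visit would disappear. That reading is hard to sustain. Section 5.1 opens the period with study procedures and closes it with study treatment, and Section 5.2 names study treatment and study participation separately. The follow-up sentence also gives a specific figure for this study, so staff would be expected to apply it. The softness points to unadapted template text rather than a deliberate choice to exclude endoscopy events, but the cut-off is still misplaced.

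**Conclusion.** The concern holds as an internal conflict with a limited practical gap. The reporting period in Section 5.1 and the serious-only sentence in Section 5.2 do not fit the visit order in Section 3.1 or Section 5.2's own each-contact rule. The clearest loss is non-serious complications arising after the endoscopy visit. The likely effect is undercounting of grade 1 and 2 events in the weekly review.

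The gap applies to every participant who has the endoscopy: 24 + 40 + 40 = 104 planned completers. How many events would be missed cannot be stated, because the documents give no complication rate. Symptom scores during the infusion are collected on study day 1 and are not affected.

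The conclusion assumes that study treatment means the study-day-1 infusion and that visits follow the listed order. If scintigraphy were done after the endoscopy, that visit would be a later contact and the gap would narrow. The change should be made; it is not a reason to doubt the trial's main analyses.

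**What to change.** Reconcile Sections 3.1, 5.1 and 5.2. In Section 5.1, define the reporting period as running from the first study procedure to a stated interval after the last study procedure, whichever visit that is. State that all adverse events in that period are recorded whatever their severity, so that Section 5.2's main duty and its each-contact rule agree. The sponsor should choose and state the interval. Delete the leftover Example label and define study treatment.

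The cost is about one sentence of protocol text and one follow-up question to each participant after the last visit.

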5.2 Recording of Adverse Events

At each contact with the subject, the study team must seek information on adverse events by specific questioning and, as appropriate, by examination. Information on all adverse events should be recorded immediately in the source document, and also in the appropriate adverse event section of the case report form (CRF). All clearly related signs, symptoms, and abnormal diagnostic, laboratory or procedure results should be recorded in the source document.

All adverse events occurring during the study period must be recorded. The clinical course of each event should be followed until resolution, stabilization, or until it has been ultimately determined that the study treatment or participation is not the probable cause. Serious adverse events that are still ongoing at the end of the study period must be followed up, to determine the final outcome. Any serious adverse event that occurs after the study period and is considered to be at least possibly related to the study treatment or study participation should be recorded and reported immediately.

5.3 Reporting of Serious Adverse Events and Unanticipated Problems

When an adverse event has been identified, the study team will take appropriated action necessary to protect the study participant and then complete the Study Adverse Event Worksheet and log. The sponsor-investigator will evaluate the event and determine the necessary follow-up and reporting required.

5.3.1 Sponsor-Investigator reporting: notifying the Mayo IRB

This section is written with the intent that a specifically designed adverse event worksheet will be completed for any SAE. The information on that worksheet will be reported to the IRB in a de-identified manner..

The IRB requirements reflect the guidance documents released by the Office of Human Research Protections (OHRP), and the Food and Drug Administration (FDA) in early 2007 and are respectively entitled “Guidance on Reviewing and Reporting Unanticipated Problems Involving Risks to Subjects or Others and Adverse Events” and “Guidance for Clinical Investigators, Sponsors, and IRBs: Adverse Event Reporting – Improving Human Subject Protection.”

(Refer to the IRB Policy and Procedure on Reporting Unanticipated Problems Involving Risks to Subjects or Others to the IRB, on the IRB web site. Describe how this will be carried out by the study team and investigator. Also address notification of other investigators if necessary.
<http://mayocontent.mayo.edu/irb/DOCMAN-0000047812>

The sponsor-investigator will report to the Mayo IRB any UPIRTSOs and Non-UPIRTSOs according to the Mayo IRB Policy and Procedures. According to Mayo IRB Policy any serious adverse event (SAE) which the Principal Investigator has determined to be a UPIRTSO must be reported to the Mayo IRB as soon as possible but no later than 5 working days after the investigator first learns of the problem/event.

The sponsor-investigator will review all adverse event reports to determine if specific reports need to be made to the IRB and FDA. The sponsor-investigator will sign and date the adverse event report when it is reviewed. For this protocol, only directly related SAEs/UPIRTSOs will be reported to the IRB.

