Data Safety and Monitoring Plan. The ultimate goal of this application is to further our understanding of GI symptoms in patients with dyspepsia and diabetes. The DSMP utilized will adhere to the protocol approved by the Mayo Clinic IRB. We propose the following plan: -

Data quality and management: The principal investigator will review all data collection forms on a three-monthly basis for completeness and accuracy of the data as well as protocol compliance.

Adverse events grading: The common grading scale listed below will be used to grade AEs:

0 No adverse event or within normal limits or not clinical significant

1 Mild AE, did not require treatment
 2 Moderate AE, resolved with treatment
 3 Severe AE, resulted in inability to carry on normal activities and required professional medical attention
 4 Life threatening or disabling AE
 5 Fatal AE

Attribution scale: An adverse event includes both, an expected side effect that is of a serious nature, or an unexpected side effect/ event regardless of severity. All events will be graded as to their attribution (unrelated to protocol, or possibly, probably, or definitely related to protocol). Any event that is reported to either the principal investigator or his designated research associates by the subject or medical staff caring for the subject and which meets the criteria will be documented as such.

Data Monitoring. The majority of data generated from these protocols will be from analyses performed in our laboratory or the immunochemical core laboratory. Standard quality control procedures are in place for each assay. The frequency of data review for this study differs according to the type of data and can be summarized in the following table:

Data type	Frequency of review
Subject accrual (adherence to protocol regarding demographics, inclusion/exclusion)	Weekly
Adverse event/safety rates (injuries)	Weekly
Annual report	Yearly for IRB

Informed Consent. Written informed consent will be obtained from all individuals who participate in the study. The principal investigator or his co-investigators meet with each participant, review the consent form in detail and confirm the subjects understanding of the study. They answer all questions posed by the participants and when convinced that the subject verbally demonstrates understanding of the protocol obtains a signed consent. Only designated staff are authorized to obtain informed consent.

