5 SAFETY AND ADVERSE EVENTS

5.1 Definitions

Unanticipated Problems Involving Risk to Subjects or Others (UPIRTSO)

Any unanticipated problem or adverse event that meets the following three criteria:

- **Serious:** Serious problems or events that results in significant harm, (which may be physical, psychological, financial, social, economic, or legal) or increased risk for the subject or others (including individuals who are not research subjects). These include: (1) death; (2) life threatening adverse experience; (3) hospitalization - inpatient, new, or prolonged; (4) disability/incapacity - persistent or significant; (5) birth defect/anomaly; (6) breach of

confidentiality and (7) other problems, events, or new information (i.e. publications, DSMB reports, interim findings, product labeling change) that in the opinion of the local investigator may adversely affect the rights, safety, or welfare of the subjects or others, or substantially compromise the research data, **AND**

- **Unanticipated:** (i.e. unexpected) problems or events are those that are not already described as potential risks in the protocol, consent document, not listed in the Investigator's Brochure, or not part of an underlying disease. A problem or event is "unanticipated" when it was unforeseeable at the time of its occurrence. A problem or event is "unanticipated" when it occurs at an increased frequency or at an increased severity than expected, **AND**
- **Related:** A problem or event is "related" if it is possibly related to the research procedures.

Adverse Event

An untoward or undesirable experience associated with the use of a medical product (i.e. drug, device, biologic) in a patient or research subject.

Serious Adverse Event

Adverse events are classified as serious or non-serious. Serious problems/events can be well defined and include;

- death
- life threatening adverse experience
- hospitalization
- inpatient, new, or prolonged; disability/incapacity
- persistent or significant birth defect/anomaly

and/or per protocol may be problems/events that in the opinion of the sponsor-investigator may have adversely affected the rights, safety, or welfare of the subjects or others, or substantially compromised the research data.

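### Section 5.3.1 contradicts itself and Section 5.1: it commits to reporting any UPIRTSO to the IRB, then limits IRB reporting to directly related events, a term the protocol never defines

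*Combined protocol and SAP*

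**What the plan says.** Four places in the combined protocol and SAP set or use a threshold of relatedness.

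- **Section 5.1, Definitions.** A UPIRTSO is "Any unanticipated problem or adverse event that meets the following three criteria". The criteria are serious, unanticipated and related, joined by AND. An event counts as related "if it is possibly related to the research procedures".
- **Section 4, Data Safety and Monitoring Plan.** Events are to be graded for attribution as "unrelated to protocol, or possibly, probably, or definitely related to protocol".
- **Section 5.2, Recording of Adverse Events.** For an SAE that arises once the study period has ended, the rule is that one "considered to be at least possibly related to the study treatment or study participation should be recorded and reported immediately". The recipient is not named.
- **Section 5.3.1, notifying the IRB.** The general commitment reads: "The sponsor-investigator will report to the Mayo IRB any UPIRTSOs and Non-UPIRTSOs according to the Mayo IRB Policy and Procedures". For an SAE judged by the Principal Investigator to meet the UPIRTSO definition, the rule is that it "must be reported to the Mayo IRB as soon as possible but no later than 5 working days after the investigator first learns" about it. The section then closes with: "For this protocol, only directly related SAEs/UPIRTSOs will be reported to the IRB".

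**The concern.** The closing sentence of Section 5.3.1 opens with words that mark it as specific to this study, and it contains *only*. A coordinator looking for the operative rule could reasonably take it as the one to apply. On its ordinary meaning, *directly related* asks for more than *possibly related*. An event could then meet the protocol's own definition of a UPIRTSO and still be held back from the IRB.

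What is at stake is participant oversight, not any estimate or test. Safety monitoring in Section 5.6 rests with the Principal Investigator, and no independent data monitoring committee is described. The mention of DSMB reports in Section 5.1 is only an example inside a definition. Prompt reporting to the IRB is therefore one of the few ways in which someone outside the study team would learn of a serious event.

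**Working it through.** No arithmetic applies, and the plan states no figure to reproduce. The check is to take a serious and unanticipated event, vary only its attribution grade, and read off what each rule requires.

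| Attribution grade (Section 4) | UPIRTSO under Section 5.1? | General commitment in Section 5.3.1 | Closing sentence of Section 5.3.1 |
|---|---|---|---|
| Unrelated | No | Not reported as a UPIRTSO | Not reported |
| Possibly related | Yes | Report; 5 working days if an SAE | Not reported, on the ordinary meaning of *directly* |
| Probably related | Yes | Report; 5 working days if an SAE | Unclear; depends on how *directly* is read |
| Definitely related | Yes | Report; 5 working days if an SAE | Reported |

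1. **Within Section 5.3.1.** The second and third columns agree in every row. The fourth departs from them at *possibly related* and is indeterminate at *probably related*.

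2. **Against the attribution scale.** The scale has four grades, and *directly related* is not among them. No other section defines it. The recorded grade therefore cannot show whether an event meets the closing sentence, and two people applying it could decide differently.

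3. **Against Section 5.2.** A possibly related SAE after the study period must be reported at once. The same event during the study might not go to the IRB if the closing sentence governs. The protocol gives no reason for a stricter filter during the study than after it.

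4. **Which events are exposed.** The three UPIRTSO criteria are joint, so the conflict with Section 5.1 concerns only events that are both serious and unanticipated. Most possibly related events, such as expected nausea during the infusion, would never be UPIRTSOs.

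5. **Other external routes.** Section 5.3.2 requires FDA reports within 7 or 15 calendar days, and the disputed sentence does not touch it. However, its rules for individual events ask for evidence of a causal link with the study drug or placebo. The study also involves fluoroscopic tube placement, duodenal lipid infusion and endoscopy with 15 duodenal biopsies (Sections 3.3 and 4). Under Section 3.1, endoscopy is on a different study day from the infusion. Harm from these procedures may not meet the drug-based test, and the IRB is then the only expedited external route described. The yearly IRB report in Section 4 is not expedited.

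**The case against.** The strongest reply is that the protocol does not adopt a rule of under-reporting. Section 5.3.1 opens by saying that an SAE worksheet will be completed for any SAE and its content sent to the IRB in de-identified form. It then commits to reporting any UPIRTSO and sets the 5-day limit. Nothing says that the last sentence supersedes these. The sentence may have been meant only for SAEs that are not UPIRTSOs, or to separate events caused by the procedures from those of the underlying disease. All adverse events in the study period must still be recorded (Section 5.2), adverse events are reviewed weekly (Section 4), and the Stopping Rules put the study on hold for perforation or clinically significant bleeding.

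Much of this stands. A reader might infer that the closing sentence overrides the general commitment. The documents do not say so; they contain conflicting instructions. A reader might also infer that IRB reporting is the main external safety check. That leaves out the FDA route, which is separate and intact.

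The lenient readings do not remove the conflict. The sentence names UPIRTSOs as well as SAEs, so it cannot be confined to SAEs that are not UPIRTSOs. Reading *directly related* as plain *related* makes the word redundant for UPIRTSOs, which are related by definition. Internal recording, weekly review and the hold rule do not replace a report to the IRB. Whether the institution's IRB policy permits such a limit cannot be checked, because the policy is not in the documents.

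**Conclusion.** The text is wrong as written. Section 5.3.1 contradicts itself and Section 5.1 on which events go to the IRB, and it does so with a term that the protocol neither defines nor records.

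The consequence is conditional. If staff apply the closing sentence in its ordinary sense, serious and unanticipated events graded possibly related could go unreported to the IRB. Those graded probably related could also be lost, but only if *directly* is taken to mean *definitely*. It would be tempting to say that two of the three related grades are lost. That counts labels rather than events, depends on that one reading, and ignores the requirement that the event also be serious and unanticipated. The number of events cannot be estimated, because the documents give no expected SAE or UPIRTSO rate.

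Confidence is high that the passages conflict. It is lower that under-reporting would follow, since that depends on which sentence staff apply. FDA reporting and the statistical analyses are unaffected.

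**What to change.** Delete the closing sentence of Section 5.3.1. Alternatively, replace *directly related* with the Section 5.1 threshold, at least possibly related, and state that the grades possibly, probably and definitely related in Section 4 all meet it. Either change brings the definition, the attribution scale and the reporting rule into agreement and leaves the 5-working-day limit as it is.

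If participants have already been studied under this wording, check the adverse event log for serious, unanticipated events graded possibly or probably related that were not sent to the IRB. The recording rule in Section 5.2 should make that check possible.

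The cost is one sentence of protocol wording. Design, sample size, procedures and analysis do not change.
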